8.1.4 Primary Efficacy Hypothesis

The primary hypothesis to be tested will be that the success rate at 2 years postoperative with the Triathlon Tritanium Cone Augments is not worse than 97.2% with a non-inferiority margin of 2.5%. That is, the following hypothesis will be tested:

Ho: Pt <= 97.2% - 2.5% HA: Pt > 97.2% - 2.5%

Here, Pt is the success rate at 2 years postoperative with the Triathlon Tritanium Cone Augments. A case success at 2 years is defined as no incidence of revision/removal of femoral or tibial cone augment for aseptic loosening within 2 years.

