8.1.5 Primary Efficacy Analysis

A 90% two-sided confidence interval will be computed for the success rate at 2 years. If the lower bound of the confidence interval is greater than 94.7%, then the non-inferiority hypothesis will be supported; that is the 2 year success rate is non-inferior to 97.2% with a margin of 2.5%. If the lower bound of the confidence interval is greater than 97.2% then it is supported that the 2 year success rate is superior to 97.2%.

The Kaplan-Meier survival curve of revision/removal of femoral or tibial cone augment will be displayed using SAS/PROC LIFETEST.

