8.4.2 Sample Size Justification

For primary efficacy objective, based on the literature review^{1,2}, it is reasonable to have a reference value of 97.2% for success rate at 2 years. A case success at 2 years is defined as no incidence of revision/removal of femoral or tibial cone augment for aseptic loosening within 2 years.

Based on Triathlon TS Outcome Study, it is reasonable to assume the expected success rate at 2 years is 98.8%, 100 cases will be needed to have a power of 80% to detect that the 2 year success rate is non-inferior to 97.2% with a margin of 2.5% at 5% significance level. After factoring a 30% lost to follow-up rate, a total of 145 cases will be needed.

For exploratory efficacy objective among cases receive the Triathlon TS Total Knee System with a Triathlon Tritanium Central Femoral Cone Augment, based on the existing data of this study for non-femoral central cone, it is reasonable to have a reference value of 86 for the mean of KSS Objective Knee Score at 2 years postoperative, with a standard deviation of 10, 32 cases will be needed to have a power of 80% to identify the mean of KSS Objective Knee Score at 2 years postoperative is Non-Inferior to 86 with a noninferiority margin of 5 at 2.5% significance level. After factoring a 30% attrition rate, a total of 46 cases will be needed.

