8.4.4 Analysis Population

Per Protocol Population: The study population for analysis will include all noncensored subjects who receive a Triathlon TS with Triathlon Tritanium Cone Augment and are available for efficacy evaluation at the 2-year primary endpoint. The primary and secondary efficacy analyses will be based on the per protocol population.

Safety Population: The safety population will include all non-censored subjects who received Triathlon TS with Triathlon Tritanium Cone Augment. The safety analysis will be based on the safety population.

9 Study Monitoring, Auditing, and Inspecting

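### The 2-year primary analysis discards the revision-free follow-up of early leavers and does not say whether failures before 2 years are counted; Kaplan-Meier in all implanted cases would settle both

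*Combined protocol and SAP*

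**What the plan says.** - **Endpoint.** In 8.1.4 a case success is "defined as no incidence of revision/removal of femoral or tibial cone augment for aseptic loosening within 2 years". The null value is 97.2% - 2.5% = 94.7%.
- **Test.** 8.1.5: "A 90% two-sided confidence interval will be computed for the success rate at 2 years". Non-inferiority is supported if the lower bound exceeds 94.7%. No interval method is named.
- **Population.** 8.4.4 restricts the per protocol set to non-censored implanted cases that "are available for efficacy evaluation at the 2-year primary endpoint. The primary and secondary efficacy analyses will be based on the per protocol population". It does not define non-censored. Appendix G has a hidden form for censoring a case from analysis, with a date and a reason, but the plan gives no rule for its use.
- **Missing data.** 8.3 rules out imputation.
- **Loss.** 8.4.2: "After factoring a 30% lost to follow-up rate, a total of 145 cases will be needed".
- **Failures.** 4.3 classes cone revision or removal for aseptic loosening as a failure. It also ends a subject's participation once all implanted cones have been revised or removed, for whatever reason.
- **Kaplan-Meier.** 8.1.5: "The Kaplan-Meier survival curve of revision/removal of femoral or tibial cone augment will be displayed using SAS/PROC LIFETEST". The sentence gives no 24-month estimate, confidence limit or decision rule, does not limit the event to aseptic loosening, and names no population of its own.

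**The concern.** Success can be scored only when 2 full years are known; failure can be scored on the day it happens. A case that is revision-free at 12 months and then dies, withdraws or is lost has no value for the endpoint, and 8.4.4 removes it together with its 12 months of information.

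What the remaining proportion estimates depends on a rule that the plan does not state.

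- **Early failures kept.** The quantity tested is failures / (failures + completers). Failures in cases that would later have been lost enter it, while the matching revision-free time of lost cases does not. Failure is overstated and power is lost.
- **Early failures dropped.** A case whose cones are all removed at 6 months is terminated under 4.3 and has no 2-year visit. If it is therefore not available under 8.4.4, failures leave the analysis and the device looks better than it is.

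With so few events expected, single failures decide the verdict, so the rule has to be fixed in advance.

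**Working it through.** **Inputs.** Null failure rate 5.3% (8.1.4); expected failure rate 1.2%, power 80%, 100 evaluable cases, 30% loss, 145 enrolled (8.4.2); 90% two-sided interval, i.e. one-sided 5% (8.1.5). The timing of loss and failure is not given, so it is assumed and varied.

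**The plan's own figure.** The one-sample arcsine formula gives n = [(1.645 + 0.842) / (2 asin√0.988 - 2 asin√0.947)]² = (2.487 / 0.2451)² ≈ 103, with power 79% at n = 100. This reproduces the 100 approximately. For loss, 100/0.7 gives 143 and 101/0.7 gives 145. The stated figures are accepted as they stand.

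**Exact decision rule.** The smallest evaluable n at which the exact lower limit exceeds 94.7% is 56, 88, 117 and 144 for 0, 1, 2 and 3 failures. At n = 100 the test passes with at most 1 failure: power 0.988¹⁰⁰ + 100 × 0.012 × 0.988⁹⁹ = 66%, type I error 2.8%.

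**Reading A: early failures counted.** Let p be the true 2-year failure probability, 30% the loss (unrelated to outcome), and a the share of failures seen before loss. The completers-only failure rate is pa / [pa + 0.7(1 - p)].

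| Loss timing | a | p = 1.2% | p = 5.3% |
|---|---|---|---|
| All losses at once after surgery | 0.70 | 1.20% | 5.30% |
| Losses and failures uniform over 2 years | 0.85 | 1.45% | 6.36% |
| All failures precede loss | 1.00 | 1.71% | 7.40% |

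Middle row at 1.2%: 0.0102 / (0.0102 + 0.6916) = 1.45%.

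**Simulation under reading A.** 145 cases, failure 1.2% and loss 30% at 24 months, loss unrelated to outcome. The first two rows use constant hazards and 6,000 trials each; the third uses uniform loss and 12,000 trials. Limits are exact; for Kaplan-Meier (KM) they use the effective sample size.

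| Loss dated | Completers: mean failure | KM: mean failure | Completers: pass | KM: pass |
|---|---|---|---|---|
| At last scheduled contact | 1.35% | 1.19% | 60% | 70% |
| Continuously | 1.44% | 1.21% | 57% | 74% |
| Uniformly over 2 years | 1.47% | 1.21% | 56% | 75% |

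At a true failure rate of 5.3%, the Kaplan-Meier version passes in about 3% of trials, below the nominal 5%. The interval method matters as much as the estimator. Under uniform loss, completers against Kaplan-Meier give 58% against 79% with Wilson limits and 82% against 93% with Wald limits, but Wald limits on Kaplan-Meier pass 9.8% of trials at 5.3% failure.

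**Reading B: early failures excluded as not available.** Observed failure is 0% whatever the truth. At a true 5.3%, about 145 × 0.7 × 0.947 = 96 cases remain, with an exact lower limit of 0.05^(1/96) = 96.9%. At a true 10%, about 91 remain and the limit is 96.8%. Both clear 94.7%.

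**The planned curve.** If it is drawn on the per protocol set, no revision-free case is censored before its 2-year evaluation. For the same event, the curve then reproduces the simple proportion and recovers nothing from early leavers.

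**The case against.** The strongest reply is that the error is small and safe. Under reading A it is about 0.15-0.25 points at the planned rate, against a 2.5-point margin, and works against the device. The 30% is a sample-size allowance, not a forecast, and 145 already pays for it. This stands, and it limits the size of the point. The allowance replaces lost cases, however; it does not use the follow-up they provided.

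A reader might infer that the plan is biased against the device by design. The documents do not support that. The direction depends on counting early failures, which 4.3 and 8.1.4 imply but 8.4.4 does not confirm. Read literally, 8.4.4 allows the opposite bias.

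A reader might also infer that the needed Kaplan-Meier estimate is already planned. Only a displayed curve is. The estimate, population, event, censoring date and limit would all be new text.

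Nor does completers-only analysis explain the whole gap from 80% power. Exact limits with 100 evaluable cases give only 66%, and 8.1.5 names no method.

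Kaplan-Meier has costs of its own. At 1.2% failure about 1.5 events are expected (145 × 0.0102), and some 23-25% of trials would have none, leaving log-log limits undefined. Death and septic cone removal are competing events that would be censored.

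Finally, 97.2% matches the average of two crude proportions in 1.1 (1/27 = 3.7% and 2/104 = 1.9%, mean 2.8% failure). The documents do not show how those series treated incomplete follow-up, so neither estimator is proven like for like with the benchmark.

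**Conclusion.** The concern holds as a modest loss of information plus an open rule. Sections 8.3 and 8.4.4 discard the revision-free time of every early leaver, and the plan does not settle whether a failure before 2 years is analysed.

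Under the reading that 4.3 and 8.1.4 favour, the bias at the planned rate is about 0.15-0.25 points (none if all losses occur at once). The cost with exact limits is roughly 10 to 17 percentage points in the chance of passing (57-60% against 70-74%). These figures assume 30% loss unrelated to outcome and depend on loss timing and interval method.

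Under the literal reading of availability, the observed failure rate tends to 0% and non-inferiority would be declared almost regardless of performance. That is the less likely reading but the more serious one. The same change removes both problems.

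**What to change.** In 8.1.5 and 8.4.4:

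1. Estimate the 2-year success rate and its 90% two-sided interval by Kaplan-Meier at 24 months, in all cases implanted with the components that 4.3 requires.
2. Count every cone revision or removal for aseptic loosening within 2 years as an event, whether or not it ends participation.
3. Censor all other cases at the last date cone status was known, and define or delete the non-censored condition.
4. Pre-specify one interval method that works with few or no events, for example exact limits on the effective sample size, not Wald. State which n applies with zero events, since the variance-based effective sample size is then undefined; the number still followed at 24 months is a cautious choice.
5. Keep the 94.7% rule.
6. Report the completers proportion, with early failures counted, as a sensitivity analysis.

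The cost is SAP wording and a few lines added to a procedure already planned; no new patients or data are needed. The downsides are reliance on loss being unrelated to outcome, and the treatment of death and septic removal as censoring. Both should be stated in the report.

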4.3 Early Withdrawal of Subjects

When and How to Withdraw Subjects

In the event that the subject is discontinued by the investigative center prior to the final study evaluation, the subject will be notified by the center that he/she is no longer in the study and a Study Termination eCRF will be completed.

The following is a list of reasons for which subjects may be withdrawn and the date of termination that should be used on the Study Termination eCRF in each situation. This list is not all inclusive:

Termination Reason	Date of Termination
Death	Date of death
Investigative center termination	Date of study close-out visit
Lost to follow-up	Date Stryker termination approval given
Voluntary withdrawal	Date subject notified center of withdrawal
Revision/removal of study device	Date of revision/removal procedure
Study device not implanted	Date of surgery
Surgery not performed	Date Stryker termination approval given

At the time of study surgery it is required that the following components are implanted to be included in the analysis:

- Triathlon Tritanium Femoral Cone Augment or Central Femoral Cone Augment and/or Tibial Cone Augment
- Triathlon TS Femoral Component
- Triathlon TS Universal Tibial Baseplate
- Triathlon TS Tibial Insert or Triathlon PS Tibial Insert

Revision or removal of the Triathlon Tritanium Cone Augments for aseptic loosening constitutes a failure. Revision or removal of all implanted Triathlon Tritanium Cone Augments for any reason requires study termination for the subject.

If revision of the Tibial Insert or the Patellar Component is required during the study, the event does not constitute a failure or study termination.

Patellar component revision at the time of study surgery is optional. However, if the subject requires patellar component revision a Triathlon Patellar Component must be used. If the patellar component is not revised at the time of study surgery and is later revised, it must be revised to a Triathlon Patellar Component. This event is considered a reoperation and does not constitute a failure or study termination.

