8.2.2 Safety Analyses

The frequency and percentage of all protocol-defined adverse events will be tabulated.

The all cause revision/removal rates for the Triathlon TS Total Knee System with Triathlon Tritanium Cone Augments will be calculated.

The Kaplan-Meier survival curve of all cause revision/removal will be displayed using SAS/PROC LIFETEST.

For details regarding protocol-defined adverse events, see Section 6.1.

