Intraoperative fissure, fracture, or perforation of the femur or tibia can occur due to impaction of the component into the prepared femur or tibia. Postoperative femoral or tibial fracture can occur due to trauma, the presence of defects or poor bone stock.

Metal sensitivity reactions have been reported following joint replacement.

AEs may necessitate reoperation, revision, arthrodesis of the involved joint, or amputation of the limb.

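### A harm that leaves the patient with no cone implanted is collected as an adverse event but drops out of the planned safety tables

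*Combined protocol and SAP*

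**What the plan says.** Section 8.4.4 defines the safety set: "The safety population will include all non-censored subjects who received Triathlon TS with Triathlon Tritanium Cone Augment". It adds: "The safety analysis will be based on the safety population". The main output is set in 8.2.2: "The frequency and percentage of all protocol-defined adverse events will be tabulated".

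Section 4.3 applies an implantation condition to analysis generally: "At the time of study surgery it is required that the following components are implanted to be included in the analysis". The first listed item is "Triathlon Tritanium Femoral Cone Augment or Central Femoral Cone Augment and/or Tibial Cone Augment", followed by the TS femoral component, the TS universal baseplate and a TS or PS insert. The termination table in 4.3 includes "Study device not implanted", with the date of surgery as the termination date. The table is introduced in permissive terms: "The following is a list of reasons for which subjects may be withdrawn and the date of termination that should be used".

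Section 11.2 recognises the kind of event at issue: "Intraoperative fissure, fracture, or perforation of the femur or tibia can occur due to impaction of the component into the prepared femur or tibia".

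No section defines a set of subjects in whom implantation was attempted.

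**The concern.** A safety denominator should be fixed by exposure to the procedure, not by how the procedure ended. Here, whether a subject is in the safety tables is settled at the end of the operation. Take two patients with the same fracture while a cone is being seated. If the first leaves theatre with a cone and the other required components, the fracture is tabulated. If the second leaves with no cone because of the fracture, both patient and fracture disappear from the tables. Inclusion depends on the outcome being measured.

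What is at stake is the completeness of the reported intraoperative and early complication rates, which sections 6.1 and 11.3 set beside published rates. This follows from the requirement that the device was received. It is separate from any question about what non-censored means.

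**Working it through.** The plan states no figure on this point, so there is nothing to reproduce. The check sets the sections side by side and then shows scale under assumed counts.

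**1. Is the subject in the safety set?** Under 8.4.4 the subject must have received the system with a cone. A subject with no cone did not. Under 4.3 a subject lacking another listed component is also not analysed. Whether the subject is formally withdrawn makes no difference, because 8.4.4 excludes a subject without a cone either way.

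**2. Who is affected?** The cone requirement in 4.3 is femoral and/or tibial. A patient whose femoral cone is abandoned but whose tibial cone is seated, or who receives a second cone after the first fails, stays in if the other components are implanted. The gap is limited to subjects left with no cone or without another required component.

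**3. Is the event captured?** Yes.
- Section 6.1 makes reportable AEs due from consent to study completion, and covers operative-site events at any time and SAEs to 90 days.
- Section 6.3 calls for 24-hour notification of intraoperative or procedure-related AEs.
- The Surgical Details form in Appendix G asks for an AE form after an intraoperative complication.
- Section 7.6 lists non-implantation of a specified component as a possible major deviation.

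The gap is in tabulation.

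**4. Can these cases be picked out afterwards?** Not reliably. Inclusion criterion C requires candidacy for full component revision, not a bone defect or a planned cone. Some subjects without a cone may simply never have needed one. In Appendix G the two cone fields on the Surgical Prostheses form carry no required-item mark, and neither surgical form has an item for a cone that was tried and not left in. A blank field does not distinguish the two situations.

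**5. Does AE follow-up continue?** Section 4.3 dates the termination to surgery. Section 6.1 runs reporting to study completion but also calls for 90-day SAEs and operative-site events without limit of time. Sections 6.1 and 6.4 follow each recorded event onward. The text does not settle whether new later events would be collected in these subjects.

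**6. Scale, under assumed counts.**
- 145 is the minimum number of implanted cases (section 2.3).
- x is the number of events of one type among implanted cases (assumed).
- k is the number of attempted cases left outside the set, each with that event (assumed 0 to 5).
- Rate as planned: x/145. Rate counting these attempts: (x + k)/(145 + k).
- Upper limit of the exact two-sided 95% interval: the 97.5% quantile of Beta(x + k + 1, 145 − x).

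| x | k | As planned (upper limit) | Counting attempts (upper limit) |
|---|---|---|---|
| 0 | 0 | 0/145 = 0% (2.5%) | 0/145 = 0% (2.5%) |
| 0 | 1 | 0/145 = 0% (2.5%) | 1/146 = 0.7% (3.8%) |
| 0 | 3 | 0/145 = 0% (2.5%) | 3/148 = 2.0% (5.8%) |
| 0 | 5 | 0/145 = 0% (2.5%) | 5/150 = 3.3% (7.6%) |
| 2 | 1 | 2/145 = 1.4% (4.9%) | 3/146 = 2.1% (5.9%) |
| 2 | 3 | 2/145 = 1.4% (4.9%) | 5/148 = 3.4% (7.7%) |
| 2 | 5 | 2/145 = 1.4% (4.9%) | 7/150 = 4.7% (9.4%) |

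Each such case adds about 0.7 percentage points. With k = 0 nothing changes.

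**The case against.** An as-implanted safety set is a reasonable choice for a single-arm, post-market study of a cleared device, and leaving out patients who never needed a cone is sensible. The events are captured and notified, and a separate listing would close the gap without redefining the population. All of this stands, and it limits the point to tabulation. It does not remove it: an AE form or a deviation record that feeds no table does not enter a reported rate.

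A reader might infer more than the documents support:

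- *That these harms are never recorded.* They are reportable, notified within 24 hours and entered on an AE form.
- *That termination on the day of surgery ends 90-day SAE collection.* No section says so. Section 4.3 says subjects may be withdrawn and fixes the date to enter; 6.1 makes no exception for subjects without a cone. The position is unclear, not settled.
- *That 11.2 names impaction fracture as a cone risk.* It sits in a list of adverse effects of revision TKA and speaks of the component generally. Section 3.1 does say that femoral and symmetric tibial cones have a feature for an impactor, so the scenario is plausible for cones, but the documents do not link it to abandoning one.
- *That the most severe device-related events are the ones removed.* Nothing links severity to abandonment.
- *That the comparison with published rates is biased in the device's favour.* The cone series summarised in 1.1 is described by cones implanted, and the documents do not say whether any comparator counted abandoned attempts. If comparators are implanted-only, adding attempts here alone would make the comparison less like with like.

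**Conclusion.** The point holds as a gap between what is collected and what is tabulated. As written, 8.4.4 and 4.3 leave out of the safety tables, in numerator and denominator, any subject in whom a cone was attempted but who left surgery with no cone or without another required component. If a harm was the reason, that harm is missing from the study's own complication rate.

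The size is unknown, because the documents give no abandonment rate. It may be nil. If such cases occur, each one with an event is worth about 0.7 percentage points on a base of 145; this assumes the minimum enrolment and one event per excluded case. The effect on the comparison with the literature cannot be determined from the documents. The primary analysis is not touched. The change is worth making because the intraoperative data are already collected and the remedy is small.

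**What to change.** 1. **Section 8.4.4.** For intraoperative and 90-day AEs, define the safety population as all enrolled subjects in whom implantation of a cone augment was attempted, whether or not it was left in place, and state what counts as an attempt. At minimum, tabulate AEs of attempted-but-not-implanted subjects separately beside the as-implanted table. Showing both keeps an implanted-only rate for comparison with the literature.
2. **Appendix G, Surgical Details form.** Add one item, cone attempted but not implanted, with the reason. This separates these cases from patients who never needed a cone.
3. **Sections 4.3 and 6.1.** Reconcile the day-of-surgery termination date with the 90-day SAE and operative-site AE collection, and state how long AEs are collected in these subjects.
4. **Primary efficacy population.** Leave unchanged.

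The cost is a sentence or two in 8.4.4, a clarification in 4.3, one eCRF item and slightly more data work. Reported complication rates may look slightly less favourable.

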17.**	Does the subject have any of the following conditions [Does subject have conditions]	[MORBIDYN] [CmpCMORBID] Yes [COMORBID] Myocardial infarction Congestive heart failure Peripheral vascular disease Cerebrovascular disease Cerebrovascular disease Dementia Chronic pulmonary disease Connective tissue disease Peptic ulcer disease Mild liver disease Diabetes without organ damage Diabetes without organ damage Hemiplegia or paraplegia Moderate or severe renal disease Malignant tumor (any) Leukemia Lymphoma Moderate or severe liver disease Metastatic solid tumor HIV
18.**	Concurrent Medical Conditions [Concurrent Medical Conditions]	[CMCYN]

			[cmpIMM] 🖃	
		-	Immunologic / Lymphatic	
			[IMM]	
			A200	
			Musculoskeletal	
			[MUS]	
			A200	
			[cmpNEUR] 🗆	
			Neurologic	
			A200	
			Psychologic	
			[PSYC]	
			A200	
			respiratory	
			A200	
			[cmpSUBD] 📃	
			Substance Dependence	
			[SUBD]	
			A200	
			A200	
			[cmpOTCMC] 🗌	
			Other	
			(Specify)	
			A200	
		No		
C	monto IDM SEI	0		
Lom	ווופות: [ככב_זעט]	DMC		
19. ✔	[Comments]			
		A200		
20.	Charlson-Deyo Comorbidity Index [read-only]	[CCI]		
		N2		
Key	: [✔] = Source verification required [b] = Base Unit []] = Item is col	lapsible		
Not Not	Note: Source verification critical settings made in InForm will override any settings made in Central Designer. Note: Collapsible settings are only available to users who have the rights to edit the item.			

TriathCone: CENSOR (CENSOR) [CENSOR]			
С	CENSOR [CENSOR]		
1.	Censor from Analysis [hidden] [Censor from Analysis]	[CENSORFA] () [cmpCENSOR] Yes [CNSRDT] Date Censored Req ↓ / Req ♥ / Req ♥ (2015-2025) [CNSREASN] Censor Reason A200	
	Key: [*] = Item is required [✓] = Source verification required Note: Source verification critical settings made in InForm will override any settings made in Central Designer.		

Tria	TriathCone: Knee Society Score: Pre-Op (PREKSS2011) [PREKSS2011]			
1.* ✔	Visit Date [Visit Date]	[KSSDOV] Req V / Req V (2015-2025)		
2.* ✓	Charnley Functional Classification [Charnley Functional Classification]	[CHARNLY] A Unilateral Knee Arthritis B1 Unilateral TKA, opposite knee arthritic B2 Bilateral TKA C1 TKR, but remote arthritis affecting ambulation C2 TKR, but medical condition affecting ambulation C3 Unilateral or Bilateral TKA with Unilateral or Bilateral THR		
Obje	ective Knee Indicators [PREKSS_S2]			

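### The safety population is limited to non-censored subjects, a term the plan never defines, so implanted patients and their events can be left out of every summary safety rate

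*Combined protocol and SAP*

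**What the plan says.** Section 8.4.4 defines two populations. For safety: "The safety population will include all non-censored subjects who received Triathlon TS with Triathlon Tritanium Cone Augment". It adds: "The safety analysis will be based on the safety population". The per-protocol population, used for the primary and secondary efficacy analyses, starts from the same filter, "The study population for analysis will include all noncensored subjects who receive a Triathlon TS with Triathlon Tritanium Cone Augment", and then adds a separate condition: the subject must be available for efficacy evaluation at 2 years.

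Section 8.2.2 lists the safety outputs: frequencies and percentages of protocol-defined adverse events, the all-cause revision/removal rate, and a curve, "The Kaplan-Meier survival curve of all cause revision/removal will be displayed using SAS/PROC LIFETEST".

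Section 4.3 has its own rule on inclusion in the analysis. It requires a study cone, the TS femoral component, the TS universal baseplate and a TS or PS insert. It does not use the word censored.

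Outside 8.4.4, censoring appears only in the draft eCRF specification in Appendix G. A CENSOR form, scheduled at the Baseline/Pre-Op visit, holds the item "Censor from Analysis [hidden] [Censor from Analysis", a censor date and a reason field, "CNSREASN] Censor Reason A200", with no coded list of reasons.

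**The concern.** A safety population normally contains everyone who was exposed, which here means everyone in whom a study cone was implanted. Section 8.4.4 adds a second condition and does not say what it means. No reason, decision-maker or time limit is given. The study is open-label and single-arm, and the sponsor manages the database (Synopsis; section 7.1), so outcomes may be known when a case is excluded.

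All three outputs in 8.2.2 inherit the filter. Protocol-defined adverse events and revision/removal rates are the study's safety parameters (8.2.1), and they are to be set against published data (6.1, 11.3). An exclusion with no stated criterion weakens those comparisons. In the per-protocol population the stakes are sharper, because at the planned size the primary test turns on one or two failures.

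**Working it through.** The plan states no figure for censored cases, so there is nothing to reproduce. The check has a textual part and two illustrations.

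**Text**

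1. Population: implanted and non-censored (8.4.4).
2. Outputs based on it: adverse event percentages, all-cause revision/removal rate, Kaplan-Meier curve (8.2.2).
3. Criteria for censoring: none in 8.4.4, none in 4.3, none in Appendix G.
4. Therefore an implanted subject can be absent from all the outputs in step 2, together with any events, under no stated rule.

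**Illustration 1: safety rate**

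Inputs: N = 145, the minimum number of cases in sections 2.3 and 8.4.2. The number of subjects with events, E, and the number of those censored, k, are assumptions. Reported rate = (E − k)/(145 − k).

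| E | k = 0 | k = 1 | k = 2 | k = 3 |
|---|---|---|---|---|
| 4 | 4/145 = 2.76% | 3/144 = 2.08% | 2/143 = 1.40% | 1/142 = 0.70% |
| 8 | 8/145 = 5.52% | 7/144 = 4.86% | 6/143 = 4.20% | 5/142 = 3.52% |
| 12 | 12/145 = 8.28% | 11/144 = 7.64% | 10/143 = 6.99% | 9/142 = 6.34% |

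Each censored subject with an event lowers the rate by about 0.6 to 0.7 percentage points.

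**Illustration 2: primary test**

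Inputs: criterion of 94.7% for the lower limit of a two-sided 90% interval (8.1.5); 100 evaluable cases (8.4.2). The plan names no interval method, so an exact (Clopper-Pearson) interval is assumed. With x successes in n, the lower limit is the 5% quantile of a Beta(x, n − x + 1) distribution.

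- 2 failures in 100: x = 98, Beta(98, 3), lower limit 93.8%. Not above 94.7%, so non-inferiority is not shown.
- One of the two failures censored, leaving 1 in 99: x = 98, Beta(98, 2), lower limit 95.3%. Above 94.7%, so non-inferiority is shown.

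The reversal does not depend on the exact method. A Wilson interval gives 94.1% and 95.6% for the same two cases. A Wald interval, p − 1.645 × √(p(1 − p)/n), moves the tipping point by one failure: 3 in 100 gives 94.2% and 2 in 99 gives 95.7%.

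**The case against.** The best defence is that the flag serves an ordinary administrative purpose. Its form is scheduled at Baseline/Pre-Op beside the eligibility and demographics forms, which fits exclusion for consent or eligibility problems, and section 7.6 lists such deviations. It could also enforce the four-component rule in 4.3: a case with a cone but a non-permitted insert may count as having received the system and still fail that rule. Hidden is a display attribute. The specification is a draft dated May 2015 that has not kept pace with the protocol: it covers no Central Femoral Cone, cleared in 2019, and its BMI exclusion is > 40 where the Synopsis has > 45. Much of this stands. The link from the flag to 8.4.4 is an inference, and nothing shows that any case was or will be removed improperly. But none of these purposes is written down as the meaning of non-censored, and none is a good reason to drop an implanted patient's events from safety.

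A reader might infer that censored means lost to follow-up, so that the planned 30% loss would leave the safety population and 8.4.4 would contradict the Kaplan-Meier analysis. The documents do not support this. The per-protocol definition lists 2-year availability separately, which would be largely redundant if non-censored already removed those lost. Loss to follow-up is recorded on a different form, Study Termination. In the strict survival sense every subject without an event is censored, so only revised subjects would remain, which the plan cannot intend.

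Nor does the rule in 4.3, "Revision or removal of all implanted Triathlon Tritanium Cone Augments for any reason requires study termination for the subject", imply exclusion. Termination ends follow-up; it does not delete the event that led to it.

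**Conclusion.** The point holds for the safety population. Section 8.4.4 places an undefined condition on top of implantation, and every output in 8.2.2 inherits it. The documents give no number of censored cases, so no single corrected rate exists. On assumed counts in 145 cases, 8 subjects with events give 5.5%, falling to 4.9%, 4.2% or 3.5% with 1, 2 or 3 of them censored. Only summary rates are affected: adverse event reporting to the sponsor and to the IRB/EC (6.1, 6.3, 6.3.1) is unchanged.

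The per-protocol filter has the same gap. There one decision can reverse the primary conclusion, given 100 evaluable cases and a failure count at the tipping point. Some exclusions can be legitimate in a per-protocol set, so that population needs defined exclusions rather than none.

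A reader might go further and take the hidden field as evidence that unfavourable cases are meant to be removed. The documents do not show that. They show a plan that permits exclusion without criteria.

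**What to change.** 1. In 8.4.4, define the safety population as all cases in which at least one study cone was implanted, with no censoring condition.
2. State that the component requirement in 4.3 for inclusion in the analysis applies to the efficacy population only. Without this sentence the new safety definition would conflict with 4.3.
3. In the per-protocol definition, replace the word noncensored with a prespecified list of coded exclusion reasons, and say who decides, when, and that the decision is made without regard to outcome.
4. List in the report every case with CENSORFA = Yes, with the date, the reason and all of its events. If the field is kept, replace the text reason with the coded list.

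The cost is a change of wording in two sections and one extra listing, with no added patients or visits. Reported safety rates may be slightly less favourable.
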